**PROTOCOL FORM / RESEARCH DESCRIPTION**

If an item does not apply to your research project, indicate that the question is "**not applicable**" – do not leave sections blank

**Click once on the highlighted entry in each box to provide your response.** Click the item number/letter or word, if hyperlinked, for detailed instructions for that question. If your response requires inserting a table, picture, etc, you may need to first delete the box that surrounds the answer and then insert your table or other special document.

**1. Purpose and objectives.** *List the purpose and objectives:*

Specific Aim 1: To assess if intubation without flexible fiberoptic bronchoscopy is possible in conventional double lumen tube (DLT) vs VivaSight DLT.

Primary Hypothesis: Cases utilizing the VivaSight will need fiberoptic bronchoscopy in 30% of cases versus 100% of cases with a conventional DLT.

Specific Aim 2: To assess the time to successful placement of the VivaSight DLT vs conventional DLT and compare the incidence of tube malposition in the two types of DLTs.

Secondary Hypothesis: The VivaSight DLT will take significantly less time to place compared with the conventional DLT. Additionally, the incidence of malposition will be significantly less with the VivaSight.

Specific Aim 3: To determine the reduction in cost associated with using VivaSight DLTs compared to conventional DLT.

Tertiary Hypothesis: Use of the VivaSight DLT will reduce the cost of fiberoptic bronchoscopy purchasing and maintenance by 50%.

**2. Background.**

- Describe past experimental and/or clinical findings leading to the formulation of your study.
- For research involving investigational drugs, describe the previously conducted animal and human studies.
- For research that involves FDA approved drugs or devices, describe the FDA approved uses of this drug/device in relation to your protocol.
- Attach a copy of the approved labeling as a product package insert or from the Physician's Desk Reference.

You may reference sponsor's full protocol or grant application (section number and/or title) or if none, ensure background includes references.

Please respond to all components of this item, or clearly indicate which components are not applicable.

**a. Background**

Thoracic surgery frequently involves single lung ventilation, which is most commonly achieved with a double lumen endotracheal tube (DLT). Double lumen tubes are more difficult to insert than single lumen tubes because they are much larger and stiffer. Malposition can lead to problems with lung deflation, difficulty with oxygenation and ventilation, or cause airway injury [1]. As auscultation alone is unreliable, the use of a flexible fiberoptic bronchoscope remains the gold standard for confirming correct placement of DLTs [2]. In one study, 35% of blindly inserted DLTs that were thought to be in correct position were found to be malpositioned upon fiberoptic bronchoscopic confirmation [3]. However, fiberoptic bronchoscopes can be costly to acquire and maintain and may not be available in all hospitals or surgical centers. The VivaSight DLT is a FDA-approved device that is indicated for use in thoracic surgical patients to provide single lung ventilation. The VivaSight DLT has an integrated camera on the distal tip of the tracheal lumen, which is attached to a screen and permits continuous visualization of its position in the trachea. In many cases, this may obviate the need to use flexible fiberoptic bronchoscopy to

IRB #	STU-2018-0098
-------	---------------

confirm correct tube placement. Previous studies have shown that time to placement for the VivaSight is significantly decreased compared to conventional DLTs [4].

Placement of the VivaSight is significantly faster than traditional DLTs because continuous visualization during insertion eliminates the need for fiberoptic confirmation in the majority of cases. Due to the continuous visualization of its position, displacement from repositioning or surgical manipulation can be detected more quickly and therefore able to be rectified faster with VivaSight DLTs. Many patients who are undergoing thoracic procedures have preexisting pulmonary disease. This compounded with the need for single lung ventilation makes these patients very intolerant to malpositioned tubes or inadequate ventilation. Being able to continuously visualize the position of the DLT may thus allow earlier identification and rectification of tube malposition for this vulnerable population of patients.

Both conventional DLT and the VivaSight DLT are made of polyvinylchloride and have similar size bronchial and tracheal cuffs. A disadvantage of the VivaSight is that if secretions or blood cover the lens, it can be difficult to dislodge and therefore the view may become obscured. It is easier to clean the tip of a fiberoptic bronchoscope since it can be removed from the airway. Based on 6 months of clinical practice at Parkland Hospital, the necessity of fiberoptic bronchoscopy use with VivaSight DLT is around 20% [unpublished data].

#### b. Current practice

The current clinical practice is to use either a conventional Mallinkrodt double lumen tube or a VivaSight DLT for thoracic cases. This is usually up to the discretion of the anesthesia faculty, as both types of tubes are readily available.

### 3. Study Design.

Describe the study design (e.g., single/double blind, parallel, crossover, etc.) Consider inserting a scheme to visually present the study design.

This prospective, randomized, comparative study is intended to enroll a total of 50 patients undergoing thoracic surgery that necessitates single lung ventilation. The efficacy and performance of the VivaSight DLT will be compared to the conventional double lumen tube. Use of fiberoptic bronchoscopy for initial tube positioning and subsequently during the case will be recorded. The attending thoracic surgeon will judge the quality of lung deflation. The occurrence of any malposition and subsequent maneuvers will be recorded. A standardized anesthetic protocol that is usual and customary for the type of operation the patient is having will be provided to the anesthesia teams of enrolled subjects. The remainder of the anesthetic care of the subject will not deviate from the standard of care.

### 4. Research Plan / Description of the Research Methods:

#### 4.a. Provide a **comprehensive narrative** describing the **research methods**.

- 1) Provide the **order in which tests/procedures will be performed**,
- 2) Provide the **setting** for these events and a description of the **methods used to protect privacy** during the study.
- 3) Provide the **plan for data analysis** (include as applicable the **sample size calculation**)

Please respond to all components of this item, or clearly indicate which components are not applicable.

#### 1) Order in which tests/procedures will be performed

##### *Screening and Informed Consent*

A member of the research team will use a screening form to look for surgical patients that meet all the inclusion and exclusion criteria. He/she will approach potential subjects in the preoperative area and the study will be explained in detail in a private room. Patients will be informed that they will receive no compensation for participating in the study and there will be no adverse consequences if they choose not to participate. If the subjects agree to participate,

informed written consent will be obtained prior to any study procedures and this document will be sent to [contact], for inclusion in the patient's medical record, per Parkland regulations. The study duration will be from the beginning of anesthesia care to postoperative (POD) 1.

#### *Anesthetic Protocol*

The anesthesia team that will be caring for the subject during surgery will be given the protocol for the study, which standardizes the general anesthetic technique.

#### *Subject Group Assignment*

A randomization schedule will be created by a member of the research team that is not involved in clinical care (i.e., statistician). Subjects will be randomized 1:1 to receive either a standard double lumen endotracheal tube or a VivaSight double lumen endotracheal tube. ETT size will be selected based on gender and height-

- A woman shorter than 5'3" should be intubated with a 35-Fr tube
- A woman taller than 5'3" should be intubated with a 37-Fr tube
- A man shorter than 5'5" should be intubated with a 35-Fr tube
- A man taller than 5'5" but shorter than 5'10" should be intubated with a 39-Fr tube
- A man taller than 5'10" should be intubated with a 41-Fr tube

Once the patient is in the operating room, they will be positioned on the operating room table and standard ASA monitors will be applied. All patients will undergo a standard anesthetic induction, which includes neuromuscular blockade.

Following induction of anesthesia, the anesthesia provider will use a direct laryngoscopy with a Mac 3 or 4 blade to visualize the glottis. Patients who have a difficult airway or who require more than 3 attempts for intubation will be excluded from the study. In the conventional DLT group, the provider will be asked to stop insertion of the tube after the tracheal lumen has passed the vocal cords. The fiberoptic bronchoscope will then be inserted into the bronchial lumen to guide the tube into the left mainstem bronchus. In the Vivasight DLT group, the tube will be connected to a monitor prior to laryngoscopy and direct visualization of the tube's position will be used to guide it into the correct position. The time that the facemask is taken off the patient's face will be recorded as the 'start time' for laryngoscopy, and the 'end time' will be when the double lumen tube is verified to be in the correct position.

Successful DLT placement will be defined as chest rise during ventilation, a square capnography waveform, bilateral breath sounds, and no air leakage. Details regarding tube placement including Cormack-Lehane grade, number of attempts, number of operations, and use of any adjunct airway devices will be recorded. An independent investigator will evaluate and record all measurements and times. The intubator will be asked to assess the procedural difficulty of intubation on a scale of 1-5- 1: very easy; 2: easy; 3: some difficulty; 4: significant difficulty; 5: impossible.

When single lung ventilation becomes necessary, the anesthesia provider will inflate the bronchial cuff and clamp the respective lumen of DLT to provide single lung ventilation. After the pleura is opened, the surgeon will be asked to rate the quality of lung collapse- 1: excellent; 2: fair; 3: poor. At the conclusion of surgery, patients who meet extubation criteria will be extubated and taken to the PACU or ICU. The duration of intubation will be recorded.

If the lens of the VivaSight becomes obscured, the anesthesia provider will be asked to take the following steps:

1. Inject 20mL air into red injection port
2. Connect 10mL syringe filled with 2 mL saline and inject (twice- total 4mL)
3. Connect 10mL syringe filled with 5-10mL of air and inject (twice)
4. Connect empty 10mL syringe and suck the saline injected (twice)
5. Confirm correct tube position with FOB.

A blinded research assistant will perform all postoperative assessments. As patient-reported outcomes have become increasingly important for hospitals, treatments that have the potential to increase patient satisfaction are being studied closely. The postoperative quality recovery scale (PQRS) is a tool that assesses recovery over time and compares them to baseline values. Some of the advantages of the PQRS are that it is validated, takes less than 5 minutes to administer, has a low patient refusal rate, and is acceptable to patients across a wide range of ages. The PQRS will be administered at baseline in the preoperative area, and after PACU arrival at 45 minutes and on POD 1 (Appendix 1).

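### The intubating provider is not fixed before the allocation is known and is not a listed data item, so operator skill can become matched to tube type, mainly in the secondary outcomes

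*Combined protocol and SAP*

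**What the plan says.** In section 4.a, Subject Group Assignment, the plan states that after induction "the anesthesia provider will use a direct laryngoscopy with a Mac 3 or 4 blade to visualize the glottis". Elsewhere in that section the same person is just the provider or the intubator. No grade, minimum experience or device training is given, nor the moment at which this person is chosen. Under Anesthetic Protocol, "The anesthesia team that will be caring for the subject during surgery will be given the protocol for the study"; what that protocol standardises is the anesthetic technique.

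On allocation, "Subjects will be randomized 1:1 to receive either a standard double lumen endotracheal tube or a VivaSight double lumen endotracheal tube", and "A randomization schedule will be created by a member of the research team that is not involved in clinical care". No concealment method, time of disclosure or stratification by operator is described. In the VivaSight group "the tube will be connected to a monitor prior to laryngoscopy".

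On data, besides the Cormack-Lehane grade, "number of attempts, number of operations, and use of any adjunct airway devices will be recorded". The Parameters list adds the times of induction and intubation and, for laryngoscopy, the view and the blade. The Statistics paragraph compares bronchoscope use by a chi-square or Fisher test with no operator term, and names no test for placement time.

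The tube-size list in the same section uses only strict comparisons, for example "A woman taller than 5'3" (that is, 5 ft 3 in).

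**The concern.** Randomising patients balances patient characteristics. It does not balance an operator who is picked after the tube type is visible. A team could, for good practical reasons, give one tube to a more experienced operator and the other to a less experienced one. Placement time and number of attempts plausibly depend on the operator, and the difficulty score is that operator's own unblinded rating. Need for the bronchoscope in the VivaSight arm may depend on the operator too: the only written instruction to use it there is the last step of the lens-clearing sequence.

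Familiarity with each tube may also differ between operators, since the plan says of tube choice in current practice: "This is usually up to the discretion of the anesthesia faculty, as both types of tubes are readily available". If operator and experience are not collected, the report cannot show whether the arms were comparable in this respect, and an Aim 2 difference in time could reflect the operator as well as the device.

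**Working it through.** **1. Order of events.** The schedule is prepared outside clinical care; the allocation reaches the team at an unstated time; the VivaSight tube is connected to its monitor; then a provider performs laryngoscopy. No step names the provider before the allocation is known. The independent investigator who records measurements and times settles who measures, not who intubates.

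**2. Primary test.** Plan inputs (Statistics): 30% versus 100%, two-sided alpha 0.05, power 90%, 25 per arm.

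- Uncorrected formula: n = [1.96 × √(2 × 0.65 × 0.35) + 1.2816 × √(0.3 × 0.7 + 1 × 0)]² / 0.7² = (1.322 + 0.587)² / 0.49 = 7.4, so 8 per arm. The plan enrols 25 per arm, with an unquantified allowance for drop-out and deviations. At 25 per arm, exact Fisher power exceeds 99.9%.
- Bronchoscope use is mandated in the conventional arm, so take 25/25 there. With k VivaSight patients not needing the bronchoscope, the two-sided Fisher p is 2 × C(25,k) / C(50,k).
- k = 6 (19/25 uses): 2 × 177,100 / 15,890,700 = 0.022.
- k = 5 (20/25 uses): 2 × 53,130 / 2,118,760 = 0.0502.
- Uncorrected chi-square remains significant up to 21/25 uses (p = 0.037).
- If the true VivaSight rate were 60%, twice the planned 30%, Fisher power would still be 97%.

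**3. Estimated VivaSight rate (illustration).** Take the 20% local experience in Background as the rate for experienced operators, and assume 40% to 60% for less experienced ones. With a share s of experienced operators, rate = 0.20s + r(1 − s).

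| s | r = 0.40 | r = 0.60 |
|---|---|---|
| 1 | 20% | 20% |
| 0.5 | 30% | 40% |
| 0 | 40% | 60% |

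**4. Placement time (illustration).** The documents give no operator effect and no standard deviation. Assume an operator effect D of 0.5 to 1.0 SD, a systematic between-arm difference of 20 to 60 points in the share of experienced operators, and no true device effect. Bias = D × difference in share. The standard error is √(2/25) = 0.283 SD. The error rate below is the normal-approximation chance that a nominal 5% two-sided test is significant.

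| D (SD) | Difference in share | Bias (SD) | Error rate |
|---|---|---|---|
| 0.5 | 0.2 | 0.1 | 6% |
| 0.5 | 0.4 | 0.2 | 11% |
| 0.5 | 0.6 | 0.3 | 19% |
| 1.0 | 0.2 | 0.2 | 11% |
| 1.0 | 0.4 | 0.4 | 29% |
| 1.0 | 0.6 | 0.6 | 56% |

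The bias could favour either tube. The table shows what selection would do if it occurred at these strengths; it does not estimate what will occur.

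**The case against.** The trial is necessarily open-label, and the plan does not mention trainees or mixed grades. A reader might infer that operator skill is already confounded with the device. The text does not support that: it permits matching and does not show it. The remark on faculty discretion concerns usual tube choice, which randomisation replaces, so it suggests only that familiarity may vary.

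A reader might also infer that the primary result is in danger. Step 2 of the working shows otherwise for significance; only the estimated VivaSight rate is exposed.

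Chance imbalance may look like further evidence. If half of intubations were by less experienced operators, two independent Binomial(25, 0.5) arms would differ by 5 or more with probability 0.20 (0.16 if the proportion were 30%). That is ordinary sampling variation, already reflected in the standard error. It is imprecision, not bias from selection.

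It would also be too strong to say that the operator is certainly unrecorded. The placement list is introduced as inclusive rather than exhaustive, the data collection sheet is not reproduced, and the anesthetic record may name the operator. The supportable statement is that operator identity and experience are not listed. Even so, prior numbers of placements with each tube would be hard to recover reliably afterwards.

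Finally, the gaps in the height bands might be read as a second route to the same bias. The sizing rule applies identically to both arms, and no link to a between-arm difference is shown.

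**Conclusion.** The point holds as a possible and preventable bias. The operator can be chosen with the allocation known, and the listed data would not reveal it. It bears mainly on placement time, attempts and the difficulty score, and on the size, though hardly the significance, of the bronchoscope result. The robustness of the primary test rests on the conventional arm following the mandated bronchoscope step. The bias from selection cannot be quantified from the documents; the ranges in steps 3 and 4 of the working rest wholly on assumed operator effects. This is a cheap improvement worth making before enrolment, not a defect that invalidates the design.

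Separately, and adding no weight to the above, the height bands leave a woman of exactly 5 ft 3 in, and a man of exactly 5 ft 5 in or 5 ft 10 in, in no band.

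**What to change.** In Subject Group Assignment, state that the intubating provider is written on the data sheet before the allocation is opened. Add to the recorded items the operator's identity or code, grade, and prior numbers of conventional and of VivaSight DLT placements. In Statistics, report Aim 2 placement time unadjusted and with one simple adjustment for operator experience, labelled supportive because there are only 25 patients per arm.

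The cost is a protocol sentence, a few data fields and less freedom to swap operators after allocation. No extra patients or staff are needed.

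As a separate drafting matter, the sponsor should reconcile the height bands so that every height falls in exactly one of them.

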**2) Setting**

The study will take place in the pre operative rooms, the operating rooms, and the PACU at Parkland Hospital.

**3) Plan for data analysis***Data Sources*

Protected health information including name, medical record number, and date of birth will be recorded and stored securely in a password-protected, secured Excel database.

*Parameters*

1. Protected health information (PHI): name, medical record number, date of birth
2. Demographic information (age, weight, height, BMI, gender), medical and surgical history, ASA)
3. Intraoperative parameters
  - Baseline vital signs upon arrival to operating room
  - Time of induction and intubation
  - Intraoperative vitals (systolic, diastolic, and mean blood pressures, heart rate)
  - Laryngoscopy details (Cormack Lehane view, blade used)
4. Adverse event monitoring
  - Airway injury
  - Patient unable to be intubated (e.g., difficult airway)
  - Prolonged hypoxia (> 1 min at <92%) from anesthesia start to anesthesia stop
  - Respiratory adverse event including bronchospasm, laryngospasm aspiration, reintubation
  - Prolonged PACU stay (> 2 hours)
  - Unplanned hospital admission

*Statistics*

The study is powered to detect a difference in the primary endpoint, the rate of fiberoptic bronchoscopy use, between 30% for the VivaSight versus 100% for the Mallinckrodt DLT. The study will have 90% power (two-sided chi-square test with type I error rate = 0.05). Accounting for patient drop out and protocol deviations, the study will enroll a total of 50 subjects (25 in each group). The continuous data will be summarized as mean and standard deviation or median and inter-quartile range, as appropriate while categorical data will be summarized as frequency and percentages. The incidence of FOB usage in the two groups will be compared using a chi-square test or Fisher's exact test. Statistical significance is set at  $p=0.05$ .

Form A

IRB #	STU-2018-0098
-------	---------------

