Intubation	
The anesthesia provider will use a direct laryngoscopy with a Mac 3 or 4 blade to visualize the glottis. Patients who have a difficult airway or who require more than 3 attempts for intubation will be excluded from the study. In the conventional DLT group, the provider will be asked to stop insertion of the tube after the tracheal lumen has passed the vocal cords. The fiberoptic bronchoscope will then be inserted into the bronchial lumen to guide the tube into the left mainstem bronchus.
	
In the Vivasight DLT group, the tube will be connected to a monitor prior to laryngoscopy and direct visualization of the tube's position will be used to guide it into the correct position. The time that the facemask is taken off the patient's face will be recorded as the 'start time' for laryngoscopy, and the 'end time' will be when the double lumen tube is verified to be in the correct position.
	
If the lens of the VivaSight becomes obscured (a risk that is not serious and less likely), the anesthesia provider will be asked to take the following steps:
 
 
1. Inject 20mL air into red injection port
 
2. Connect 10mL syringe filled with 2 mL saline and inject (twice- total 4mL)
 
3. Connect 10mL syringe filled with 5-10mL of air and inject (twice)
 
4. Connect empty 10mL syringe and suck the saline injected (twice)
 
5. Confirm correct tube position with FOB.
 

DLT Placement	
Successful DLT placement will be defined as chest rise during ventilation, a square capnography waveform, bilateral breath sounds, and no air leakage. Details regarding tube placement including Cormack-Lehane grade, number of attempts, number of operations, and use of any adjunct airway devices will be recorded. An independent investigator will evaluate and record all measurements and times. The intubator will be asked to assess the procedural difficulty of intubation on a scale of 1-5- 1: very easy; 2: easy; 3: some difficulty; 4: significant difficulty; 5: impossible.
		

Form A

IRB #	STU-2018-0098
-------	---------------

	Single Lung Ventilation	When single lung ventilation becomes necessary, the anesthesia provider will inflate the bronchial cuff and clamp the respective lumen of DLT to provide single lung ventilation. After the pleura is opened, the surgeon will be asked to rate the quality of lung collapse- 1: excellent; 2: fair; 3: poor.		
2	Eligibility Assessments			

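### Excluding patients who need more than 3 intubation attempts acts after allocation, so the placement-time and difficulty results leave out late or failed placements, and no analysis set covers them.

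*Combined protocol and SAP*

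**What the plan says.** Section 4.a, Subject Group Assignment, randomises patients 1:1 to a conventional or a VivaSight double lumen tube. It then states: "Patients who have a difficult airway or who require more than 3 attempts for intubation will be excluded from the study". The Intubation row of table 4.d repeats that patients who "require more than 3 attempts for intubation will be excluded from the study".

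The same section shows that the arm is fixed before any attempt is counted. In the VivaSight group "the tube will be connected to a monitor prior to laryngoscopy".

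The placement clock starts when the facemask comes off, and its end time "will be when the double lumen tube is verified to be in the correct position". Success has its own definition, which begins: "Successful DLT placement will be defined as chest rise during ventilation". The number of attempts is recorded, and the intubator grades difficulty on a five-point scale that ends "4: significant difficulty; 5: impossible".

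The secondary hypothesis in section 1 is that "The VivaSight DLT will take significantly less time to place compared with the conventional DLT". Section 4.a.3, Parameters, lists as an adverse event "Patient unable to be intubated (e.g., difficult airway". Section 4.a.3, Statistics, mentions drop-out and protocol deviations only as a reason for enrolling 50 patients. It names a between-group test for bronchoscopy use and nothing else.

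**The concern.** Ease of placement is part of what the trial compares. A rule that removes patients because placement took too many attempts selects on something the allocated tube may influence, and it does so after randomisation. The placements removed are the slow and failed ones, which matter most to a claim that one tube is quicker to place. If one tube fails more often, the time comparison would not show it, because its failures are not in it.

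The plan is also inconsistent about these patients. It provides a difficulty grade and an adverse event for intubations that do not succeed, yet it takes such patients out of the study. A placement that is never verified has no end time, and no rule says what value it takes.

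**Working it through.** **1. Timing.** A count above 3 requires attempts, and attempts are made with the allocated tube. This half of the exclusion therefore follows allocation on any reading. The difficult-airway half could be a screen before randomisation, or a finding at laryngoscopy after it; the text does not say which.

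**2. The plan's own figure.** The only stated size is 25 per arm, for 30% versus 100% bronchoscopy use at 90% power and two-sided 0.05. With mean proportion 0.65:

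n = [1.96 × √(2 × 0.65 × 0.35) + 1.282 × √(0.3 × 0.7)]² / 0.7² = (1.322 + 0.587)² / 0.49 ≈ 7.4, so 8 per arm, or 11 with continuity correction.

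The figure of 25 is not reproduced without an unstated allowance of 1 − 22/50 = 56% to 1 − 16/50 = 68%. That is a separate matter. At 25 per arm, power for the primary endpoint is above 99.9%. For placement time the plan gives no expected value, SD, test or power.

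**3. How truncation distorts a comparison (success rates assumed).** Let each attempt succeed with probability p, and q = 1 − p. The excluded share is q³. Mean attempts are 1/p in all patients, and (p + 2pq + 3pq²)/(1 − q³) in those kept.

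- p = 0.8: excluded 0.8% (0.2 of 25); mean 1.25 in all, 1.216/0.992 = 1.23 in those kept.
- p = 0.6: excluded 6.4% (1.6 of 25); mean 1.67 in all, 1.368/0.936 = 1.46 in those kept.

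The difference between tubes falls from 0.42 to 0.24 attempts. At 0.9 versus 0.7 it falls from 0.32 to 0.24, and at 0.7 versus 0.5 from 0.57 to 0.23. With equal success rates there is no distortion. In mean time, if an ordinary placement takes 100 s and an affected one 300 s (assumed), keeping k affected patients gives (300k + 100(25 − k))/25 = 100, 108 and 116 s for k = 0, 1, 2. Each affected patient moves the arm mean by 8 s.

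**4. Sensitivity of the time test (all inputs assumed).** Mann-Whitney test, two-sided 0.05, 25 per arm, log-normal times, VivaSight to conventional median ratio 0.7, SD of log time 0.5, 40,000 simulations. Power in %:

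| Affected (VivaSight, conventional) | Excluded | Never verified, worst rank | Late, own time × 3 |
|---|---|---|---|
| 0, 0 | 67 | 67 | 67 |
| 1, 0 | 66 | 53 | 56 |
| 2, 0 | 66 | 37 | 44 |
| 0, 1 | 66 | 73 | 72 |
| 0, 2 | 65 | 78 | 78 |
| 1, 1 | 65 | 60 | 62 |
| 2, 2 | 63 | 53 | 57 |

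With exclusion, power stays at 63–67% whichever arm the failures fall in. With the patients kept, it responds to where they fall.

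**5. Range of the cost.** Two never-verified placements in each arm, excluded versus worst rank, at other assumed inputs:

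- ratio 0.6, SD 0.5: about 90% to 85%
- ratio 0.7, SD 0.3: about 97% to 94%
- ratio 0.8, SD 0.5: about 29% to 21%
- ratio 0.8, SD 0.3: about 66% to 57%
- ratio 0.6, SD 0.3: above 99% either way

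The loss is about 2 to 10 points, and negligible where power is already near 100%.

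**6. Primary endpoint.** Take 7 VivaSight patients with bronchoscopy use, close to 30% of 25. After exclusion of 1 or 2 VivaSight patients: 7/24 or 7/23 against 25/25, Fisher p = 5.3e-8 and 1.1e-7. With everyone kept: 7/25 to 9/25 against 25/25, p at most 8.3e-7; 9/25 against 23/25, p = 7.1e-5.

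**7. Failure counts.** 2/25 against 0/25 gives Fisher p = 0.49. A comparison of failures by arm can only be descriptive.

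**The case against.** Exclusion from the study need not mean that data already collected are thrown away. The plan records attempts, adjunct devices and a top difficulty grade, and it monitors failed intubation as an adverse event, so data on these patients seem to be expected. This stands in part: the text does not settle the matter. But removal is the plain reading of the rule, and no other section overrides it.

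Nor is a difference between arms shown. Both arms use the same laryngoscope blades, and the Background describes tubes of the same material with similar cuffs. If an attempt means passing the vocal cords, a count above 3 may largely reflect the patient's anatomy. That also stands as a limit: the term is undefined and the direction of any bias is unknown. It does not exclude an effect of the tube, since the VivaSight camera is live from the start.

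The simulations rest on assumed times and counts, and power does not itself measure bias. Agreed; they show sensitivity only. Worst rank is one reasonable rule among several. Time-to-event analysis with censoring, or failures reported by arm beside observed times, would also close the gap.

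Three stronger inferences are tempting and unsupported. One is that the exclusion favours the VivaSight: the documents give no failure rate for either tube. Another is that it undermines the primary result: step 6 shows otherwise. The third is that only failures beyond 3 attempts are lost: the difficult-airway half of the same sentence may remove others after allocation, and with attempts undefined the boundary is unclear.

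**Conclusion.** The point holds and should be fixed, at the level of the secondary aim. As written, the time comparison and difficulty scores describe only patients intubated within 3 attempts, and possibly only those without a difficult airway found at laryngoscopy. A difference between tubes in late or failed placement would not appear in them. The exclusion, the difficulty scale and the adverse-event list must be reconciled.

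The size of any bias cannot be derived from the documents. If no patient exceeds 3 attempts and none is found after allocation to have a difficult airway, nothing changes. If one or two do in arms of 25, the time result can move either way under the assumptions shown. The primary bronchoscopy conclusion is very unlikely to change. The same patients also leave the malposition comparison; no estimate is offered for that.

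**What to change.** In Subject Group Assignment and table 4.d, replace the exclusion from analysis with: *All randomised patients are analysed in their allocated arm; patients needing more than 3 attempts, or found after randomisation to have a difficult airway, stay in the analysis and are reported by arm.*

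In Statistics, before any data are seen:

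- Use the observed time wherever the allocated tube is eventually verified in position.
- Pre-specify one rule for placements never verified, for example worst rank with a rank test.
- Score bronchoscopy use as it occurred; counting failed placements as bronchoscopy used is a sensitivity analysis only.
- Report failures by arm descriptively, including in the safety data, and define an attempt.

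Clinical handling is unchanged.

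The cost is one sentence in each of two places and a few in Statistics, with no extra patients. Times, bronchoscopy use and adverse events must go on being recorded for these few patients, which the documents do not now state. The time result may also look less favourable. With 2 never-verified placements per arm, the power loss is at most about 10 percentage points in the settings worked. It is larger if failures fall only in the VivaSight arm: 66% to 37% with two such failures at ratio 0.7 and SD 0.5.
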